1.1.3. Signs and Symptoms

The clinical picture of MMM involves constitutional symptoms (e.g., cachexia, night sweats, bone pain, fatigue, fever—present in 40% of subjects), splenomegaly, anisopoikilocytosis with teardrop erythrocytes, progressive anemia, immature myeloid and erythroid precursors in the peripheral blood (in one-third of the subjects), elevated lactate dehydrogenase (LDH) levels, and fibrosis of the marrow (as evaluated by reticulin and trichrome [collagen] stains). The leukoerythoblastic picture is postulated to be related to both the intramedullary sinusoidal marrow and splenic hematopoiesis.

The disease generally occurs in adults, 70% of the subjects are over the age of 50 years and the median age ranges from 54 to 62 years. Anemia is apparent in 50% to 70% at diagnosis and 25% will have severe anemia with hemoglobin level < 8.0 gm/dL. Splenomegaly is present in 85% to 100% of the subjects at diagnosis, and is massive in 10%. Approximately half of the subjects present with an elevated white cell count (WBC), 28% with thrombocytosis (platelet count $> 500 \times 10^9$ /L, and 37% with thrombocytopenia (platelet count $< 150 \times 10^9$ /L).

Growth factor and cytokine variations are multiple. It is unclear whether the aberrations in cytokine production and in the vasculature are pathogenic or whether they represent a nonspecific reaction associated with the underlying clonal activity. Increased levels of basic fibroblast growth factor (bFGF) have been reported in subjects with MMM. Both transforming growth factor—beta (TGF-beta) and bFGF regulate cell growth and differentiation. In addition to their potent fibrogenic activity, TGF-beta and bFGF regulate hematopoiesis by selective actions on primitive stem cells. Basic FGF has been shown to augment the activity of stem cell factor (SCF), interleukin-3 (IL-3), granulocyte-macrophage colony stimulating factor (GM-CSF), or erythropoietin on committed progenitor cells. Serum interleukin-6 (IL-6) has multiple biological effects, including the regulation of hematopoiesis, immune responses, and acute phase reactions. IL-6 appears to be a potent megakaryocytic maturation factor. Other cytokines/proteins that are disregulated in MMM include; tumor necrosis factor-alpha (TNF-alpha) and angiogenic agents like vascular endothelial growth factor (VEGF).

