3.3.1. Key Inclusion Criteria

Subjects must meet all of the following inclusion criteria to be eligible for enrollment into the study:

- Must be ≥ 18 years of age at the time of voluntarily signing an Institutional Review Board/Independent Ethics Committee (IRB/IEC) – approved informed consent form.
- 2. Must be diagnosed with myelofibrosis requiring therapy including myelofibrosis with myeloid metaplasia (MMM), de novo presentation (i.e. agnogenic myeloid metaplasia [AMMM], and developing after an antecedent history of Polycythemia vera (i.e., post-polycythemic myeloid metaplasia [PPMM]), or essential Polycythemia (i.e., post thrombocythemic myeloid metaplasia [PTMM]).
- 3. Screening total hemoglobin level < 10 g/dL or transfusion-dependent anemia defined as per IWG criteria (transfusion dependency defined by a history of a least 2 units of red blood cell transfusions in the last 28 days for hemoglobin < 8.5 g/dL that was not associated with overt bleeding).
- 4. Must have adequate organ function as demonstrated by the following \leq 14 days prior to starting study drug:
 - ALT (SGOT) and AST(SGPT) \leq 3 x upper limit of normal (ULN), [unless upon judgment of the treating physician, it is believed to be due to extramedullary hematopoiesis (EMH)]
 - Total bilirubin < 3 x ULN or Direct Bilirubin < 2 x ULN
 - Serum creatinine $\leq 2.5 \text{ mg/dL}$
 - Absolute neutrophil count $\geq 1,000/\mu L \ (\geq 1.0 \times 10^9/L)$
 - Platelet count $\geq 50,000/\mu L \ (\geq 50 \times 10^9/L)$
- 5. Subjects must be willing to receive transfusion of blood products.
- 6. ECOG performance status (PS) of 0, 1, or 2 at screening.
- 7. Must be willing to adhere to the study visit schedule and other protocol requirements.
- 8. No active malignancies with the exception of basal cell or squamous cell carcinoma of the skin, or carcinoma "in situ" of the cervix or breast.
- 9. All study participants must be registered into the mandatory POMALYST REMSTM program, and be willing and able to comply with the requirements of the POMALYST REMSTM program.
- 10. Females of reproductive potential (FCBP[†]) must adhere to the scheduled pregnancy testing as required in the POMALYST REMSTM program. Able to take

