3.6.2. Initiation of a New Cycle of Therapy

A new course of treatment may begin on the scheduled Day 1 of a new cycle if:

- The ANC is $\geq 1,000/\mu L (\geq 1 \times 10^9/L)$;
- The platelet count is $\geq 50,000/\mu L \ (\geq 50 \times 10^9/L)$;
- Any CC-4047-related allergic reaction/hypersensitivity or sinus bradycardia/ other cardiac arrhythmia adverse event that may have occurred has resolved to ≤ grade 1 severity;
- Any other CC-4047-related adverse event that may have occurred has resolved to ≤ grade 2 severity

If these conditions are not met on Day 1 of a new cycle, the subject will be evaluated weekly and a new cycle of CC-4047 will not be initiated until the toxicity has resolved as described above.

3.6.3. Instructions for dose modifications or interruption during a cycle.

Table 1: CC-4047 Dose Modification Guidelines

CTCAE CATEGORY	ADVERSE EVENTS	DOSING CHANGE
Allergy/Immunology	Allergic reaction/ hypersensitivity (including drug fever) Grade 2	Discontinue CC-4047.
	Allergic reaction/ hypersensitivity (including drug fever) Grade 3	Discontinue CC-4047.
Blood/ Bone Marrow	Neutropenia ANC < 500/μL (Grade 4) for >7 Days	Discontinue CC-4047.

CTCAE CATEGORY	ADVERSE EVENTS	DOSING CHANGE		
Blood/Bone Marrow	Thrombocytopenia Platelet count < 25,000/μL (Grade 4) for >7 Days	Discontinue CC-4047.		
Cardiovascular	Thrombosis/Embolism Grade 3 or 4	Hold CC-4047 and start systemic anticoagulation. Restart at the same dose level at investigator's discretion and only if approved by the Principal Investigator based on established significant benefit to the patient. The patient must sign consent form again to restart the therapy.		
Dermatology/Skin	Grade 3 Rash	Discontinue CC-4047.		
	Desquamating/Blistering Rash	Discontinue CC-4047.		
	Rash: Erythema multiforme	Discontinue CC-4047.		
Endocrine	Elevated or Reduced Thyroid Function Test results without symptoms of hyper- or hypo- thyroidism	Confirm test results. If significar refer for appropriate therapy. Maintain dose of CC-4047 if appropriate.		
	Elevated or Reduced Thyroid Function Test results with symptoms of hyper- or hypo- thyroidism	Hold study drug. Evaluate etiology and refer for appropriate therapy. Restart at the prior dose.		
Neurology	Neuropathy – Cranial/motor/sensory Grade 2	Hold CC-4047. Restart once adverse event is completely resolved.		
	Neuropathy – Cranial/motor/sensory Grade 3	Discontinue CC-4047.		
	Neuropathy – Cranial/motor/sensory Grade 4	Discontinue CC-4047.		

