Toxicity: As per NCI CTCAE Version 3.0, the term toxicity is defined as adverse events that are classified as either possibly, probably, or definitely related to study treatment. Such adverse events will be captured by Principal Investigator and his staff in a database. The maximum grade for each type of toxicity will be recorded for each subject, including start/stop dates, and frequency tables for each group will be reviewed to determine toxicity patterns. In addition, we will review all adverse event data that is graded as 3, 4, or 5 and classified as either "unrelated or unlikely to be related" to study treatment in the event of an actual relationship developing.

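### Hematologic toxicity is summarized only as the maximum related grade, without reference to baseline, although every subject enters with anemia or transfusion dependence and reduced platelets and neutrophils are permitted

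*Combined protocol and SAP*

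**What the plan says.** Section 5.3.3 (Toxicity) first restricts what is counted: "the term toxicity is defined as adverse events that are classified as either possibly, probably, or definitely related to study treatment". It then gives the summary: "The maximum grade for each type of toxicity will be recorded for each subject, including start/stop dates, and frequency tables for each group" are to be reviewed for patterns. Events classed as unrelated or unlikely to be related get a separate look if severe: "we will review all adverse event data that is graded as 3, 4, or 5". The toxicity text mentions no baseline grade, worsening from entry, treatment-emergent definition or shift table. The same section does plan change from baseline for quality of life.

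On entry, criterion 3 in section 3.3.1 requires "Screening total hemoglobin level < 10 g/dL or transfusion-dependent anemia defined as per IWG criteria". Criterion 4 sets floors of 1,000/µL for neutrophils and 50,000/µL for platelets. Table 1 (section 3.6.3) shows where grade 4 lies: "Neutropenia ANC < 500/μL (Grade 4) for >7 Days" and "Platelet count < 25,000/μL (Grade 4) for >7 Days".

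Safety is one of the two primary endpoints in section 2.2.1. Section 5.4 includes everyone who received any study drug in the safety analyses. Section 3.1 provides a complete blood count with differential at screening, weekly counts for the first 56 days, and counts at least every 28 days after that.

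**The concern.** A maximum grade tells the reader how low a count went, not how far it fell. In subjects who all start with low hemoglobin, or depend on transfusion, an on-study anemia grade may only restate the entry condition. The same holds, to a lesser degree, for platelets and neutrophils above the entry floors.

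Reduced platelet counts at entry are realistic. Section 1.1.3 reports platelets below 150 × 10⁹/L in 37% of patients. The dose-finding trial of this drug described in section 1.2 had a median of 111 × 10⁹/L, and its update mentions 5 of 19 subjects starting at 50 to 100 × 10⁹/L.

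The study is open-label with no concurrent control, so no background rate can be subtracted and baseline is the only internal reference. Section 1.2 reports that myelosuppression was dose-limiting and that 13 of the first 20 subjects in this study had it at 3 mg/day. The toxicity stopping rule in section 5.4 does not cover hematologic events, so the descriptive table is where study-level hematologic safety will be read.

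**Working it through.** The plan states no figure that depends on this point, so there is nothing to reproduce. The check has two parts.

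**1. Which tables can be affected.** Entry criteria against the grade 4 levels in Table 1:

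| Lineage | Allowed at entry | Grade 4 level in Table 1 | Grade 4 possible at entry? |
|---|---|---|---|
| Neutrophils | ≥ 1,000/µL | < 500/µL | No |
| Platelets | ≥ 50,000/µL | < 25,000/µL | No |
| Hemoglobin | < 10 g/dL or transfusion-dependent | not given | Cannot be judged from the documents |

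Grade 4 neutropenia or thrombocytopenia on study therefore represents a fall below the entry floor. Lower grades in these two lineages, and anemia in general, can be present at entry. The documents do not give the full CTCAE cut-offs, so no grade is assigned here to a hemoglobin below 10 g/dL or to the two floors.

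**2. How much attribution matters.** For one lineage, let
- b = share already at grade 3 or higher at entry,
- f = share of those whose event is judged at least possibly related,
- q = rate of new grade 3 or higher events among the rest, all taken as judged related.

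Expected share in the table = b·f + (1 − b)·q. Share with a new event = (1 − b)·q.

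The documents give neither b nor f for this study, so both are varied. q = 5% is assumed. N = 37, the evaluable target in section 5.3.2, is used for scale only, since the safety set is all treated subjects.

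| b | New events, 37·(1 − b)·q | Table, f = 0 | Table, f = 0.5 | Table, f = 1 |
|---|---|---|---|---|
| 0 | 1.9 | 1.9 | 1.9 | 1.9 |
| 10% | 1.7 | 1.7 | 3.5 | 5.4 |
| 25% | 1.4 | 1.4 | 6.0 | 10.6 |
| 50% | 0.9 | 0.9 | 10.2 | 19.4 |

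Example for b = 25%, f = 0.5: 0.25 × 0.5 + 0.75 × 0.05 = 0.1625, and 37 × 0.1625 = 6.0.

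With b = 0 attribution of entry cytopenia is irrelevant. That is the position for grade 4 neutropenia and thrombocytopenia. With b above zero the tabulated count can range from exactly the new events to mostly entry disease.

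**The case against.** The case on the other side is substantial.

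- **Attribution filter.** Stable pre-existing anemia does not enter the table automatically. It enters only if an investigator calls it at least possibly related. Start and stop dates are kept, and severe events called unrelated are also reviewed, which guards against under-attribution. This stands and narrows the point. It does not close it: the plan gives no rule for attributing a pre-existing cytopenia, dates show timing rather than entry grade, and the review has no stated output on worsening.
- **The main toxicities.** A reader might infer that anemia is the main expected toxicity and that entry disease swamps it. The documents do not support this. In section 1.2 they name neutropenia and thrombocytopenia for CC-4047. The 50% rate of grade 3-4 anemia there belongs to lenalidomide with prednisone. The rates at 0.5 mg/day are low: grade 3-4 thrombocytopenia 2% and neutropenia 0% as a single agent (58 patients), and grade 3 or higher 9% and 5% with prednisone (22 patients).
- **A tempting count.** Section 1.1.3 says "25% will have severe anemia with hemoglobin level < 8.0 gm/dL", and a reader might apply this to the trial: 0.25 × 37 = 9.25, or about 9 subjects. That does not follow. The 25% describes patients at diagnosis, not trial entrants; 37 is the efficacy target, not the safety set; the documents do not map that hemoglobin level to a grade; and all of these subjects would have to be judged drug-related to reach the table.
- **No decision depends on it.** The stopping rule counts only grade 4 cardiac, lung, liver or neurological events. New-cycle and discontinuation criteria use absolute counts. The efficacy rule uses responses. All of this stands.
- **Limits of a shift table.** Progressive anemia is part of the disease and transfusions are allowed, so worsening is not the same as drug toxicity. This is a good reason to supplement the relatedness-based table and not to replace it.

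**Conclusion.** The point holds as a minor one. Section 5.3.3 gives no way to tell entry cytopenia from on-treatment worsening in the anemia table or in the lower-grade neutropenia and thrombocytopenia tables. How far the two are mixed depends on the unknown entry grades and on investigator judgment. Under the assumed inputs the excess runs from none to several times the new events, and the documents do not allow a narrower statement. Grade 4 neutropenia and thrombocytopenia can be read as planned, given that entrants meet the floors. The operating characteristics, the interim and final efficacy rules and the toxicity stopping rule are unaffected. The point deserves action because safety is a primary endpoint, there is no control group, and the data for a clearer summary are already collected.

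**What to change.** Keep the planned table of maximum related grade. Add to section 5.3.3 a shift table for hemoglobin, neutrophils and platelets, with these features:

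- baseline grade (defined, for example, as the last count before the first dose) against worst on-study laboratory grade;
- all subjects who received any study drug, by cohort;
- regardless of attribution;
- the number and proportion who worsened by at least one grade, for each lineage.

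Add a sentence that hemoglobin shifts also reflect disease progression and transfusion, so they should not be read as drug effect alone.

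The cost is one extra descriptive table and a few lines of SAP text. The screening and on-study counts already supply the data. Sample size, decision rules, stopping rule and treatment of subjects do not change.

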5.4 Safety evaluation

Data from all subjects who receive any study drug will be included in the safety analyses. Subjects who entered the study and did not take any of the study drug and had this confirmed, will not be evaluated for safety.

The severity of the toxicities will be graded according to the NCI CTCAE v3.0 whenever possible.

Toxicity Stopping Rule:

This phase II clinical trial will have a stopping rule based on toxicity defined as an adverse event considered to be at least possibly related to treatment. In particular accrual to the study will be temporarily suspended if: a) 2 or more among the first 10 subjects treated on this trial experiences a Grade 4 cardiac, lung, liver or neurological toxicity that is felt to be drug related. b) 20% or more of subjects (when more than 10 subjects have been accrued) experience a Grade 4 cardiac, lung, liver or neurological toxicity that is felt to be drug related. After consideration by the study team (study chair[s], statistician, etc.) a decision will be made as to whether accrual can resumed.

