In addition, results of randomized Phase II study have been published (Tefferi, 2009). In a phase II randomized, multicenter, double-blind, adaptive design study, four treatment arms were evaluated: pomalidomide (2 mg/day) + placebo, pomalidomide (2 mg/day) + prednisone, pomalidomide (0.5 mg/day) + prednisone, and prednisone + placebo. Pomalidomide was administered for up to twelve 28-day treatment cycles. Prednisone (30 mg/day) was given in a tapering dose schedule during the first three cycles. Response was assessed by International Working Group criteria. Eighty four patients with MMMassociated anemia were randomly assigned to the above-listed treatment arms: 22, 19, 22 and 21, respectively. All active patients have completed six cycles of treatment. Response in anemia was documented in 20 patients, including 15 who became transfusionindependent. Response rates in the four treatment arms were 23%, 16%, 36% and 19%. The corresponding figures for patients receiving ≥ 3 cycles of treatment (n=62) were 38%, 23%, 40% and 25%. Response to pomalidomide ± prednisone was durable (range 3.2-16.9+ months) and significantly better in the absence of leukocytosis (37% vs. 8%; p=0.01); JAK2V617F or cytogenetic status did not affect response. Grade ≥ 3 toxicities were infrequent and included (in each treatment arm) neutropenia (9%-16%-5%-5%), thrombocytopenia (14%-16%-9%-5%) and thrombosis (9%-5%-0%-0%). Pomalidomide therapy at $0.5 \pm an$ abbreviated course of prednisone is well tolerated in patients with myelofibrosis and active in the treatment of anemia.

Finally, 20 patients have been accrued into current study so far, with starting dose of 3mg/day. After median follow up of 2 months, most patients had to interrupt the therapy due to side effects: 13 patients experienced myelosuppression, 3 had rash/swelling. The study accrual has been put on hold, pending modification of the dose to 0.5mg/day (given continuously).

ADDENDUM 3/30/11:

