Finally, preliminary interim results of this study are available, as described in section 5.5: 20 evaluable patients have been observed for at least 6 cycles on therapy with single agent CC-4047 at 0.5mg/day. We have observed 3 patients that has become transfusion independent (response rate of 15%). In terms of toxicity, the therapy with such a low dose of pomalidomide was very safe: one occurrence of neutropenic fever and one occurrence of leg DVT (both in the same patient). Therefore, we propose to study low dose pomalidomide 0.5mg/day in combination with prednisone, to extend previously noted activity of the combination (22 patients treated with 36% response rate) as reported by Tefferi (2009).

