5.3.2. Study Design

Subjects receiving CC-4047 alone, and the new study cohort of patients receiving CC-4047 and prednisone in combination will be evaluated using the same statistical design: a two stage design with one interim analysis will be used to permit early reporting of efficacy results if there is strong evidence that the study regimen is inactive. 37 evaluable subjects will be accrued onto this study unless undue toxicity is encountered. We anticipate accruing an additional 10-20% of subjects to account for ineligibility or cancellation; i.e. we may accrue as many as 70 subjects to this study. Subjects who have been taken off study due to toxicity related to high dose pomalidomide (i.e. those who started therapy with 3mg/day) will be replaced with new patients that will start therapy with 0.5mg/day), so that the goals of the study can be accomplished.

• Decision Rule: If 3 or fewer treatment successes are observed after all 37 evaluable subjects have been followed for at least 6 cycles, we will conclude that the treatment is insufficiently active in this subject population. If 4 or more treatment successes are observed, then this will be considered adequate evidence of promising activity, and the treatment may be recommended for further testing in subsequent studies.

- Over accrual: if more than the target number of subjects are accrued, the additional subjects will not be used to evaluate the stopping rule or used in any decision making process. However, they will be included in final point estimates and confidence intervals.
- Study duration: The anticipated accrual rate for this group of subjects is approximately 3 subjects per month. It will take approximately 14 months to accrue 37 evaluable subjects. The analysis can begin as soon as the 37th evaluable subject has been observed for 6 cycles (168 days), i.e., approximately 20 months after the trial opens.

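### The 2-in-10 toxicity check was used up by subjects on CC-4047 alone, so as written it cannot operate for the CC-4047 plus prednisone cohort

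*Combined protocol and SAP*

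**What the plan says.** The toxicity stopping rule in section 5.4 has two parts. Either one suspends accrual temporarily while the study team reviews.

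- Part (a) is met when "2 or more among the first 10 subjects treated on this trial experiences a Grade 4 cardiac, lung, liver or neurological toxicity" considered drug related.
- Part (b) is met when "20% or more of subjects (when more than 10 subjects have been accrued) experience a Grade 4 cardiac, lung, liver or neurological toxicity" considered drug related.

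Neither part names a regimen, starting dose or cohort.

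The trial's history is in the addenda to section 1.2. The addendum of 11/10/09 reports that "20 patients have been accrued into current study so far, with starting dose of 3mg/day". The addendum of 3/30/11 reports that "20 evaluable patients have been observed for at least 6 cycles on therapy with single agent CC-4047 at 0.5mg/day", and on that basis says "we propose to study low dose pomalidomide 0.5mg/day in combination with prednisone".

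Section 5.3.2 was updated for the change of regimen: "the new study cohort of patients receiving CC-4047 and prednisone in combination will be evaluated using the same statistical design". It also says "we may accrue as many as 70 subjects to this study". For toxicity, section 5.3.3 adds only that "frequency tables for each group will be reviewed to determine toxicity patterns".

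**The concern.** Section 2.1.1 makes the safety of CC-4047 plus prednisone a primary objective, and section 5.4 holds the only numeric boundary on accrual for toxicity. Part (a) guards the first exposures to a regimen. Tied to the first 10 subjects on the whole trial, it guarded a regimen no longer being enrolled. Section 3.7.2 itself warns that thrombosis risk may rise when CC-4047 is given with steroids such as prednisone, so the protocol does not treat single-agent safety as fully transferable.

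Part (b) does not clearly fill the gap. Pooled over all subjects, its denominator is swollen by people who never took the combination. Counted by cohort, it is silent until more than 10 have been accrued.

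**Working it through.** **Plan's own figures.** The plan gives no operating characteristics for the toxicity rule. Its efficacy figures in section 5.6 (significance level 0.09 at a 5% success rate, power 0.91 at 20%) reproduce as 0.0898 and 0.9100 by exact two-stage binomial, but they do not bear on this point.

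**Who the first 10 subjects were.** The first 20 accrued started CC-4047 at 3 mg/day. Prednisone was proposed only after 20 evaluable single-agent 0.5 mg/day subjects had at least 6 cycles of follow-up. No combination subject can therefore be among the first 10 treated.

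**Inputs and assumptions.**

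- Combination cohort: 37 subjects (section 5.3.2).
- Earlier subjects, m: assumed 20 to 33, where 33 = 70 − 37. The documents do not say how far the two groups of 20 overlap. If they do not overlap at all, m = 40.
- Earlier qualifying events, e: assumed 0. The addenda report myelosuppression, rash/swelling, a neutropenic fever and a leg DVT, and nothing in the four listed organ classes.
- The rule is checked after every combination subject, with each outcome known. Section 5.4 sets no look schedule.

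**Trigger after n combination subjects with k events.**

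- Both parts by cohort: k ≥ 2 for n ≤ 10, then k/n ≥ 0.20.
- Part (b) only, by cohort: no check for n ≤ 10, then k/n ≥ 0.20.
- Part (b) pooled: (k + e)/(m + n) ≥ 0.20.

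**Events needed at n = 10 with e = 0.** By cohort, 2. Pooled with m = 20: 0.20 × 30 = 6. With m = 33: 0.20 × 43 = 8.6, so 9. With m = 40: 0.20 × 50 = 10, that is, every subject.

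**First 10 subjects at a true 20% rate.** By cohort: 1 − 0.8^10 − 10 × 0.2 × 0.8^9 = 1 − 0.107 − 0.268 = 0.624. The other figures come from an exact binomial recursion that stops at the first trigger.

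| Counting | First 10, 20% rate | Over 37, 20% rate | Over 37, 30% rate |
|---|---|---|---|
| Both parts by cohort | 0.624 | 0.809 | 0.979 |
| Part (b) only, by cohort | 0 | 0.76 | 0.973 |
| Pooled, m = 20 | 0.0065 | 0.103 | 0.546 |
| Pooled, m = 33 | <0.0001 | 0.012 | 0.209 |
| Pooled, m = 40 | <0.0001 | 0.002 | 0.083 |

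**Sensitivity to earlier events** (pooled, over 37, 20% rate). With 1, 2 or 3 earlier events: 0.21, 0.38 or 0.62 for m = 20, and 0.03, 0.07 or 0.15 for m = 33.

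**The case against.** The best counter-argument is that section 5 leaves all its counts unqualified. The 20 and 37 evaluable subjects of the efficacy design name no cohort either, and they apply to the combination only through the same-design sentence in section 5.3.2. With toxicity tables promised by group, a by-cohort restart of section 5.4 is a fair guess at the intent. But the same-design sentence goes on to define a two-stage design with one interim analysis for efficacy, and the tables carry no boundary. Neither restarts the toxicity count, so the intent has to be written down.

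The second argument is about size, and part of it stands. The largest contrasts need the pooled reading. If part (b) is by cohort, it counts events from the first 10 as soon as the eleventh subject is accrued, and 3 of 11 triggers it. At a true 20% rate it has then tripped with probability 0.38 by subject 11 and 0.60 by subject 15, against 0.62 and 0.70 with both parts by cohort. In that reading the loss is mainly early.

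Third, the documents give no sign that rates of 20% or 30% are likely here. Section 1.2 describes grade 3 or higher toxicity as infrequent in the published randomised study that included 0.5 mg plus prednisone (22 patients in that arm). That is fair, but a stopping rule has to be judged at the rates it exists to catch.

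Other safeguards remain: SAE reporting, the undue-toxicity clause in section 5.3.2, termination rights in section 6.5 and the individual discontinuation rules in Table 1. None sets a numeric limit on accrual.

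**Conclusion.** The concern holds and should be fixed. Followed as written, part (a) gives the combination cohort no protection, whichever way part (b) is read. At a true 20% rate, the chance of suspension within the first 10 combination subjects falls from 0.62 to 0.0065 or less (pooled) or to 0 (part (b) by cohort). Over the full cohort the size depends on the reading: 0.81 falls to between 0.10 and 0.012 if pooled with 20 to 33 earlier subjects, but only to 0.76 if part (b) is by cohort.

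That part (a) is spent follows from the documents alone. The probabilities also rest on the assumed number of earlier subjects, no earlier qualifying events and a check after every subject. More earlier subjects would worsen the dilution; earlier qualifying events would lessen it.

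A separate, minor wording point: both parts specify Grade 4, so read literally a fatal drug-related event in a listed organ class would not count. The main conclusion does not depend on this.

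**What to change.** In section 5.4, state that both parts are counted within the CC-4047 plus prednisone cohort, starting from its first treated subject. Part (a) would then cover the first 10 subjects treated in that cohort. Part (b) would use that cohort's subjects as its denominator once more than 10 have been accrued to it. Keep the present 2-in-10 and 20% thresholds and the four organ classes. For the minor point, write Grade 4 or 5 in both parts.

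This takes two sentences. The price is more review holds when true toxicity is below the threshold. Over 37 subjects, the hold probability becomes 0.10 at a true 5% rate, 0.33 at 10% and 0.60 at 15%, against about 0, 0.001 and 0.02 when pooled with 20 earlier subjects and no earlier events. These are the properties of the plan's own thresholds applied to the regimen under study, and a hold is a temporary review, not a termination.

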3.7.2. Anticoagulation Consideration

CC-4047 may increase the risk of thrombotic events in subjects who are at high risk or with a history a thrombosis, in particular when combined with other drugs known to cause thrombosis. When CC-4047 is combined with other agents such as steroids (e.g. dexamethasone, prednisone), anthracyclines (Doxil, adriamycin) and erythropoietin the risk of thrombosis may be increased.

Subjects must receive oral low-dose aspirin (81 mg) as prophylactic anti-thrombotic treatment unless it is contraindicated or the subject has a platelet count less than $75,000/\mu$ L. If low-dose aspirin is contraindicated, the investigator should prescribe another appropriate prophylactic anti-thrombotic therapy.

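### The toxicity stopping rule counts Grade 4 events only, so read literally a drug-related death in the same organ classes does not count toward suspending accrual

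*Combined protocol and SAP*

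**What the plan says.** Section 5.4 (Safety evaluation) introduces a "stopping rule based on toxicity defined as an adverse event considered to be at least possibly related to treatment". The next sentence narrows this to two limbs, either of which temporarily suspends accrual until the study team has reviewed the position:

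- Limb (a): "2 or more among the first 10 subjects treated on this trial experiences" a qualifying event.
- Limb (b): a cumulative 20% or more of subjects, once more than 10 have been accrued.

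The qualifying event is the same in both. In limb (b) the subjects must "experience a Grade 4 cardiac, lung, liver or neurological toxicity that is felt to be drug related". One grade is named, and four organ classes.

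Section 5.3.3 (Toxicity) says of Grade 3 to 5 events judged unrelated or unlikely to be related: "we will review all adverse event data that is graded as 3, 4, or 5". It also has the maximum grade of each toxicity type recorded for each subject.

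**The concern.** A stopping rule is applied by counting records that match its definition. Here the definition names Grade 4 and nothing above it. A fatal event is Grade 5 and does not match, so the most serious outcome in a listed class is the one left out of the count.

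The recording convention in section 5.3.3 sharpens this. If only the maximum grade per toxicity type is kept, a toxicity that passes through Grade 4 and ends in death is stored as Grade 5. A tally of Grade 4 records would miss it.

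Safety is a primary objective (section 2.1.1) and a primary endpoint (section 2.2.1), and no other provision ties a count of events to suspension of accrual. The clause in section 5.3.2 on undue toxicity has no criterion attached. The rule should therefore not depend on a generous reading where deaths are concerned.

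**Working it through.** **What the text covers.** In section 5.4, both limbs name Grade 4, with no wording for higher grades. In section 5.3.3, Grades 3, 4 and 5 are listed separately. The plan thus names Grade 5 in one place and not in the other, and nothing links the two.

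**Is there a stated figure to reproduce?** Not for this rule: the plan gives no operating characteristics for it. The two-stage efficacy table in section 5.6 was recomputed as the sum over x = 2 to 20 of P(X1 = x | n = 20) × P(X2 ≥ max(0, 4 − x) | n = 17). It agrees with the plan: 0.0898 against 0.09 at a 5% response rate and 0.910 against 0.91 at 20%. Stopping at stage I is 0.736 and 0.069, against 0.74 and 0.07. Those figures are not in question.

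**Thresholds of the toxicity rule.** Limb (a) needs 2 events within the first 10 patients. Limb (b) needs events ≥ 0.2n for n > 10: 3 at n = 11, 4 at n = 20 and 8 at n = 37.

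**Limb (a) alone.** With p the true proportion of patients having a counted event,

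P(at least 2 of 10) = 1 − (1 − p)^10 − 10p(1 − p)^9.

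At p = 0.10: 1 − 0.3487 − 0.3874 = 0.264. At p = 0.05: 0.086.

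**Both limbs.** Let f_n(k) be the probability of having reached patient n with k events and no suspension. Then f_n(k) = (1 − p)·f_{n−1}(k) + p·f_{n−1}(k − 1). Mass is removed as suspended when k ≥ 2 for n ≤ 10, or k ≥ 0.2n for n > 10. At p = 0.10 the chance of suspension by n = 37 is 0.330, so limb (b) adds 0.330 − 0.264 = 0.066.

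**As written against Grade 5 counted.** Let p4 and p5 be the proportions of patients whose worst related event in the four classes is Grade 4 or Grade 5. As written p = p4; with Grade 5 counted p = p4 + p5. All rates below are assumptions, because the documents give none.

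| p4 | p5 | Suspension by 37, as written | Suspension by 37, Grade 5 counted |
|---|---|---|---|
| 0 | 10% | 0 | 0.33 |
| 0 | 20% | 0 | 0.81 |
| 5% | 5% | 0.10 | 0.33 |
| 2% | 5% | 0.02 | 0.18 |
| 2% | 1% | 0.017 | 0.037 |

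Three further assumptions apply: patients are independent, the rule is checked after each patient, and the count starts at the first of the 37. The plan does not say whether the count restarts for the prednisone cohort.

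**The case against.** **The team surely meant Grade 4 or higher.** That is likely, and the lead-in covers any adverse event at least possibly related to treatment. A patient who dies may also have had a Grade 4 phase first. But the operative sentence narrows the lead-in, no text says or higher, and the maximum-grade record would hide the Grade 4 phase. This objection makes the correction uncontroversial; it does not make it unnecessary.

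**A related death would be acted on anyway.** Much of this stands. Section 4.1 sends all serious adverse events to the IND Office, with a written report by the next working day for unexpected, related fatal or life-threatening events. Section 4.1.1 requires every serious event to reach the company within 24 hours. Section 5.3.3 reviews toxicity frequency tables, and section 6.5.2 allows the study to be ended for medical reasons. A reader might infer that deaths, or thrombosis, go unmonitored, and the documents contradict that. The gap is only in the numerical trigger.

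**A stronger charge is tempting.** A reader might infer that the trial's own history shows the rule failing, since at 3 mg/day "13 patients experienced myelosuppression, 3 had rash/swelling" among 20 patients and neither event type is on the list. The documents do not support that inference:

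- No grades are given, so these counts cannot be set against a limit for Grade 4 events. Nor is it said that the 13 and the 3 are different patients.
- Section 1.2 says accrual was put on hold. It does not say how that was decided, or whether the present rule was then in force.
- That dose has been abandoned. For 0.5 mg/day with prednisone (22 patients), section 1.2 reports Grade 3 or higher neutropenia in 5%, thrombocytopenia in 9% and thrombosis in 0%. For 0.5 mg/day alone (58 patients), Grade 3 or 4 thrombocytopenia and neutropenia were 2% and 0%.

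**Nor must the list match Table 1.** Section 3.7.2 warns that when CC-4047 is combined with agents such as steroids, anthracyclines and "erythropoietin the risk of thrombosis may be increased", and Table 1 (section 3.6.3) has an entry for "Thrombosis/Embolism Grade 3 or 4". But Table 1 governs individual dosing and section 5.4 governs accrual, so the two do not conflict. Leaving marrow toxicity out of a trial-level rule is defensible where 37% of patients have thrombocytopenia at diagnosis (section 1.1.3) and disease and drug effects are hard to separate.

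**Conclusion.** The point holds for Grade 5. As worded, related fatal events in the four listed classes contribute nothing to either limb of the only numerical accrual-suspension rule. This rests on a literal reading; if the team already applies the rule as Grade 4 or higher, the text is simply incomplete.

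The size depends on assumed event rates. With 10% related Grade 5 events and no Grade 4 events, suspension by 37 patients moves from 0 to about 0.33. With 5% of each, it moves from about 0.10 to 0.33. At the low rates one would hope for, both figures are small.

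The point does not extend to a finding that haematological or thrombotic events must be added, and the 3 mg/day counts are no measure of its size for 0.5 mg/day plus prednisone. One ambiguity remains: Table 1 files thrombosis and embolism under the cardiovascular category, so it is unclear whether a Grade 4 event of that kind counts as cardiac or lung under section 5.4.

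**What to change.** In section 5.4, limbs (a) and (b), replace *Grade 4* with *Grade 4 or 5* (equivalently, Grade 4 or higher). The thresholds and organ classes stay as they are.

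The cost is one phrase in each limb and a slightly higher chance of a temporary pause that the study team can lift after review. With 2% Grade 4 and 1% Grade 5 events, for example, the chance of a pause by 37 patients goes from 0.017 to 0.037.

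Optionally, the team could add a sentence saying whether the omission of haematological and thrombotic events from the trial-level rule is deliberate, and whether Grade 4 thrombosis or embolism counts as cardiac or lung. Those are the clinical team's decisions; no class or limit is proposed here.
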